	14.4.1 Informed Consent/Assent Process (in Case of a Minor)39
14.5	Exclusion of Women, Minorities, and Children (Special Populations)39
14.6	Participant Confidentiality39
14.7	Study Discontinuation40
14.8	Future Use of Stored Specimens40
15	Data Handling and Record Keeping.....41
15.1	Data Management Responsibilities41
15.2	Data Capture Methods.....41
15.3	Types of Data.....41
15.4	Timing/Reports.....42
15.5	Study Records Retention42
15.6	Protocol Deviations42

Table of Contents

	page
16 Publication Policy	44
17 Literature References	45
Appendix A - Schedule Of Events	53

AE	Adverse Event/Adverse Experience
BCR	B-cell immunoglobulin receptor
CFR	Code of Federal Regulations
CIOMS	Council for International Organizations of Medical Sciences
CRF	Case Report Form
CoC	Certificate of Confidentiality
DMID	Division of Microbiology and Infectious Diseases, NIAID, NIH,
DHHS	Department of Health and Human Services
DSMB	Data and Safety Monitoring Board
FWA	Federal Wide Assurance
GCP	Good Clinical Practice
ICF	Informed Consent Form
ICH	International Conference on Harmonization
IEC	Independent or Institutional Ethics Committee
IFN γ	Interferon Gamma
IL-2	Interleukin 2
IRB	Institutional Review Board
Kg	Kilogram
ILI	Influenza-like illness
LAR	Legally authorized representative
MOP	Manual of Procedures
N	Number (typically refers to participants)
NIAID	National Institute of Allergy and Infectious Diseases, NIH, DHHS
NIH	National Institutes of Health
OCRA	Office of Clinical Research Affairs, DMID, NIAID, NIH, DHHS
OHRP	Office for Human Research Protections
ORA	Office of Regulatory Affairs, DMID, NIAID, NIH, DHHS
PBMC	Peripheral blood mononuclear cells
PI	Principal Investigator
SAE	Serious Adverse Event/Serious Adverse Experience
SMC	Safety Monitoring Committee
SOP	Standard Operating Procedure
TNF α	Tumor Necrosis Factor Alpha
WHO	World Health Organization

PROTOCOL SUMMARY

Title: Effect of frequency and type of influenza vaccination on the development of the anti-influenza CD4 T cell and B cell response in children

Population: 220 children enrolled at between 6 months and 15 years of age vaccinated with the seasonal IIV (cohort A) or between 3 months and 15 years of age with an acute influenza infection (cohort B)

Number of Sites: One site

Study Duration: 3.5 years

Participant Duration: 2 influenza seasons in the main study plus 1 optional season

Objectives:

Primary Objective

To evaluate the relationship between influenza virus exposure through infection and vaccination and CD4 T cell reactivity in a cohort of children with well documented influenza exposures

Primary Outcome Measures:

- Assess the frequency and functional potential of CD4 T cell responses on a single cell level using full spectrum flow cytometry following either infection or inactivated influenza vaccine administration, with stratification by age and exposure history

Exploratory Objectives

[figure not shown]
Determine the durability and breadth of the CD4 T cell and B cell/antibody responses and evaluate for relationships between response durability and factors such as age and exposure history.

Exploratory Outcome Measures:

[figure not shown]
- Evaluate the humoral immune response that develops in response to infection or IIV vaccination using ELISA, microneutralization, and HAI assays with stratification by age and exposure history
- Determine the frequency of influenza-specific plasmablasts and memory B cells by ELISPOT and flow cytometry, with expression of monoclonal antibodies from cloned variable genes of single cells
- Determine the influence of the CD4 T cell response on the breadth and avidity of the post-vaccination antibody response
- Compare the cellular phenotype and functional potential observed at the day 24 post vaccination visit in study year one with that present at the prevaccination study visit in year 2 and year 3

Study Schematic

- **Cohort 1A and 1B: Children between 3 and 12 months of age (6 months of age or greater required for participation in the vaccination cohort 1A)**

- **Cohort 2A and 2B: Greater than 12 months of age, birth date after 2009 (early exposure to pH1N1)**
 - Cohort 2A will enroll 35 children <3 years of age and 25 children >=3 years of age
- **Cohort 3A and 3B: Birth date between 2006 and 2009**
- **Cohort 4A and 4B: Birth date between 2003 and 2006 (early exposure to previous seasonal H1N1 strains)**

2 BACKGROUND INFORMATION AND SCIENTIFIC RATIONALE

2.1 Background Information

Current guidelines recommend yearly influenza vaccination for all children ≥ 6 months of age [1]; however the effect this has on the evolution of the anti-influenza immune response through childhood and into adulthood is poorly understood. Though far from ideal, yearly vaccination is necessary at present due to the ongoing antigenic drift that occurs as viruses continually evolve to evade neutralizing antibody. There is currently much interest in the development of a universal influenza vaccination that would be able to provide protection against both seasonal and potentially pandemic strains of influenza [2]. However, a growing body of evidence suggests that early childhood influenza exposures result in imprinting that profoundly shapes lifelong CD4 T cell and B cell mediated immunity to this virus [3,4]. An improved understanding of immunity to influenza virus in early childhood is thus needed if a more broadly protective approach to influenza vaccination is to be successful.

Natural influenza infection stimulates vigorous inflammation with activation of multiple pattern recognition receptors. This leads to a robust innate immune response characterized by production of antiviral cytokines such as interferons that both limit early viral replication and instruct developing adaptive immunity [5-8]. As the infection progresses, viral replication results in abundant intracellular antigen that can be processed and presented to activate the adaptive immune response [5,6]. While neutralizing antibodies are thought of as the major correlate of protection [9-12], cellular immunity is increasingly recognized as important in protecting from severe disease [13-16], especially as T cells can recognize conserved epitopes and provide some degree of protection in years when antigenic drift leads to a poor vaccine match or a pandemic influenza strain emerges [17-21]. In contrast to the robust responses that develop following influenza infection, the immune response generated on vaccination with IIV is characterized by weak inflammatory signaling. IIV is produced by chemical inactivation of the H1N1, H3N2, and influenza B viral strains predicted to be circulating with disruption and purification of the surface glycoproteins (HA and NA) [22-24]. This process results in production of an unadjuvanted vaccine that contains variable levels of NA, small amounts of internal virion proteins including NP, and only trace amounts of innate immune activators such as viral RNA [22,25-27].

Given the profound differences in antigenic context between natural infection and vaccination, this study will investigate how these different routes of early childhood exposure to influenza affect the functional potential of the anti-influenza immune response and determine the consequences this has on subsequent influenza vaccination. This improved knowledge of how early childhood influenza vaccination shapes the establishment of anti-influenza immunologic memory will enable both optimization of current influenza vaccination strategies and development of novel vaccines able to provide highly efficacious universal protection against both seasonal and potentially pandemic influenza strains.

2.2 Scientific Rationale

This protocol is a population-based study that will address the hypothesis that vaccination and infection differentially drive both the CD4 T cell and B cell immunity. Recent data in the literature [3,4,28], and our own preliminary data suggest that initial encounters with influenza have a long lasting effect on both CD4 T cell and B cell mediated immunity. This protocol will address how early immunity against influenza virus is primed by vaccination versus infection and whether this differentially poises subsequent immune responses on re-challenge with influenza vaccination. We will specifically test whether the more robust pro-inflammatory response initiated on first exposure to a natural influenza infection promotes imprinting of both CD4 T cell and B cell responses, influencing long term specificity and functionality. We also will examine the effects of age and exposure on the immune response that develops following influenza vaccination. To do this, we will first examine whether early exposure to a live viral infection compared to vaccination leads to a distinct phenotype and specificity in both the B cell and CD4 T cell compartments. Subsequently, we will determine whether the CD4 T cell repertoire is remodeled over time by examining CD4 T cell specificity, cytokine production, and expression of markers and transcriptional factors associated with a negative regulatory CD4 T cell phenotype in children of different ages versus adults.

The age range of the first cohort was chosen to enroll infants in their first influenza season with no history of prior exposure to influenza virus. Thus, this age cohort will allow examination of the true primary response to influenza infection or inactivated vaccination. Children between 6 and 12 months of age who have not previously had an influenza infection or vaccination will be eligible to participate in vaccination cohort 1A. During Visit 1, they will have an initial prevaccination blood draw and will then receive a dose of inactivated influenza vaccine. These children will then receive a booster dose of the inactivated influenza vaccine, with vaccine doses separated by 28 (+ 14) days as recommended by the AAP. A post vaccination blood draw will only be performed following the second vaccine dose [1]. To minimize blood draws, we will perform the next blood draw to interrogate the immune response following the second vaccine dose. Children between 3 and 12 months of age who present with an influenza-like illness will be eligible to participate in the infection cohort (1B). Study personnel will obtain nasal swabs from potential subjects for a rapid influenza antigen test on illness presentation (typically this occurs at day 2-4 post illness onset) if influenza testing was not completed by the clinical microbiology lab. In the event that influenza testing result is pending or completed by a medical provider, results of this test will be obtained through review of the medical record. If positive, subjects will be eligible for further study participation. Given the low sensitivity of rapid influenza testing, influenza real-time RT-PCR will be used to confirm all rapid antigen test results, with subjects recruited for further study participation if RT-PCR testing is positive. In addition, if the subject is eligible for enrollment based on a positive influenza test result by the clinical microbiology laboratory and symptomatic at the time of presentation, a nasal swab for additional influenza real time RT-PCR testing may be obtained during the first study visit (study visit 1, or visit 2 if visit 1 is bypassed) in order to obtain further information regarding the infecting influenza serotype if possible.

The age ranges of the subsequent cohorts were chosen to capture the likely exposure histories of enrolled children, specifically surrounding exposure to the 2009 pandemic H1N1 virus. All of

the children in cohorts 2 through 4 of the vaccination arm of the study will have previously received at least 2 doses of influenza vaccine, and thus will only require a single vaccine dose. However, children presenting with acute influenza infection may not yet have received 2 vaccine doses and thus may require both a priming and a booster dose of vaccine in year 2 of the study [29]. The second age cohort (> 12 months, birthdate after 2009) will likely have had exposure to the 2009 pandemic virus in early childhood. The third age cohort (birthdate between 2006 and 2009) may or may not have had early exposure to the 2009 pandemic virus, while the final cohort (birthdate between 2003 and 2006) will likely have had early childhood exposures to the previously seasonal H1N1 viral strains.

Blood draws will be obtained on study enrollment, day 8 (+2d), and day 24 (+/- 4d) post enrollment as depicted in Figure 1. The blood draw on study enrollment will evaluate influenza-specific immunity at the time of study entry. The blood draw on day 8 (+2d) post-vaccination will allow examination of each subject as CD4 T cell and plasmablast responses are peaking, while the day 24 (+/- 4d) time point will capture the peak of the neutralizing antibody response and allow us to examine CD4 T cell responses as they contract. All subjects will be followed through to the subsequent influenza season, at which point they will be rechallenged with IIV. Blood draws will again be obtained pre-vaccination and at days 8 (+2d) and 24 (+/- 4d) post vaccine administration, with the pre-vaccination blood draw providing a method to assess for undocumented influenza infection over the prior year. Upon completion of the planned follow up visits, subjects will be offered the opportunity to participate in the study for an additional influenza season to enable collection of longitudinal data on the development of early life anti-influenza immunity.

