5.1 Inclusion Criteria

- Age
 - Between 6 and 12 months at the time of enrollment to participate in the vaccination arm of age cohort 1A
 - Between 3 and 12 months at the time of enrollment to participate in the natural infection arm of age cohort 1B
 - > 12 months, birth date after 2009 for either the vaccination (A) or natural infection (B) arm of age cohort 2
 - Birth date between 2006 and 2009 for either the vaccination (A) or natural infection (B) arm of age cohort 3
 - Birth date between 2003 and 2006 for the vaccination (A) or natural infection (B) arm of age cohort 4
- Gestational age of ≥ 37 weeks at birth
- Parent/LAR can provide informed consent, with children ≥ 8 years of age providing informed assent
- Available for the duration of the study
- History of previous primary IIV vaccination (at least 2 previous doses for age <9 yrs, at least 1 previous dose for age 9 and older) **ONLY** for participation in the vaccination (A) arm of age cohorts 2, 3, or 4

- Acute illness documented by rapid influenza test, PCR testing, or testing done by either URM Labs or RGH Clinical Microbiology Labs to be due to influenza virus **ONLY** for participation in the natural infection arms (B) of age cohorts 1-4
- Children enrolled in the Cohort A (vaccination cohort) are required to have an appropriate weight and vital signs as determined by a licensed medical provider. Children enrolled in the Cohort B (natural infection cohort) are required to have an appropriate weight and clinically stable vital signs as determined by a licensed medical provider.
 - Children will not qualify for study participation if their weight is more than 2.5 standard deviations below population norms. This will be determined through calculation of a Z score using the PediTools website (<https://www.peditools.org/>) utilizing the appropriate CDC growth calculators for age [32].

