11 STATISTICAL CONSIDERATIONS

11.1 Study Hypothesis

The primary hypothesis being tested in this study is that there will be differences in the specificity, magnitude and functionality of CD4 T cell and B cell reactivity in a cohort of young children depending on early childhood exposures.

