Here y_{kit} represents the k th response variable measured from the i th subject at the t th time point; α_k is the overall mean value of y_{kit} ; $G(i)$ is a binary variable which equals 0 if the i th subject is vaccinated with IIV and 1 otherwise; β_{1k} is a linear coefficient that quantifies the magnitude of the group-effect; β_{2k} are linear coefficients for potentially confounding clinical variables listed above; γ_{kt} is a random effect term that quantifies the time effects; and $\dot{\mathbf{0}}_{kit}$ represents independent measurement errors. Likelihood ratio test will be used to test $H_0 : \beta_k = 0$ against $H_1 : \beta_k \neq 0$.

In case of high-dimensional data in different scales, standardization will be applied before model fitting and variable selection. Variable selection approaches using AIC or BIC criteria will be used to select the significant predictors. Penalized-based variable selection procedures such as LASSO [39] or SCAD [40,41] may be used to overcome the drawbacks of ad-hoc methods of stepwise, best subset selection, etc. post-hoc.

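### The question is how immunity is primed, but the group term G(i) codes the enrolment event; only cohort 1 is designed as a first exposure and it supplies about a fifth of a common coefficient

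*Combined protocol and SAP*

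**What the plan says.** **The question.** Section 2.2 says: "This protocol will address how early immunity against influenza virus is primed by vaccination versus infection". Section 11.1 expects differences in "reactivity in a cohort of young children depending on early childhood exposures".

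**Who can answer it.** Section 2.2 gives the first-exposure role to cohort 1: "this age cohort will allow examination of the true primary response to influenza infection or inactivated vaccination". For the rest of the vaccination arm, the "children in cohorts 2 through 4 of the vaccination arm of the study will have previously received at least 2 doses of influenza vaccine". Section 5.1 makes this an entry rule for 2A to 4A: "History of previous primary IIV vaccination (at least 2 previous doses for age <9 yrs", with at least one dose from age 9. No such rule applies to 2B to 4B. Section 5.2 admits vaccine failures to the B cohorts, and Section 2.2 notes that some infected children may have had fewer than two doses. Likely early exposure in cohorts 2 to 4 is inferred from birth date, not from arm.

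**What is tested.** In model (0.1), G(i) is 0 if the "subject is vaccinated with IIV and 1 otherwise". There is one group coefficient per response, with a likelihood ratio test. The named covariates are age, sex, asthma or allergies, other illnesses and medications. Section 11.4 also plans time-specific tests across ages and influenza exposures, and general linear models of change from baseline. The primary outcome (Section 3.2.1) is to be stratified by age and exposure history.

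**The concern.** All children are to receive IIV in season 2, so G(i) can only sensibly mean the enrolment arm. In cohort 1 that is intended to be the first exposure. In older children it need not be: a 13-year-old infected at enrolment is coded 1 even if the first influenza antigen that child met was a vaccine.

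A single coefficient across all four cohorts therefore blends two contrasts: route of first exposure (cohort 1) and, for the most part, type of most recent exposure in children with a history (cohorts 2 to 4). If they differ, the coefficient can be significant with no priming effect, or can dilute a real one. Section 11.4 does not say which of its analyses answers the priming question, so nothing in the plan prevents the common coefficient from being read as that answer.

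**Working it through.** **Inputs from the documents (Section 5).** Arm A: 20, 60, 30, 30 in cohorts 1 to 4. Arm B: up to 20 in each.

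**Reproducing the plan's total.** 20 + 60 + 30 + 30 = 140; 4 × 20 = 80; 140 + 80 = 220, as stated. Cohort 1 is 40 of 220 (18%); cohorts 2 to 4 are 180 (82%).

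**Assumptions.** Section 11.2 gives no SD, effect size or power. I take one response at one time point, SD 1, two-sided 5% without FDR adjustment, and full enrolment. The effects below are illustrations.

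**Weight of each cohort.** In a common group coefficient adjusted for cohort, the weight is w = nA × nB / (nA + nB):

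| Cohort | nA | nB | w | Share |
|---|---|---|---|---|
| 1 | 20 | 20 | 10 | 20.4% |
| 2 | 60 | 20 | 15 | 30.6% |
| 3 | 30 | 20 | 12 | 24.5% |
| 4 | 30 | 20 | 12 | 24.5% |

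The sum is 49, so SE = 1/√49 = 0.143. Cohorts 2 to 4 hold 39/49 = 79.6%.

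**Case A: zero effect in cohort 1, effect d in cohorts 2 to 4.** Common coefficient = d × 39/49; z = d × 39/7; rejection probability = Φ(z − 1.96).

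| d (SD) | Coefficient | z | Rejection |
|---|---|---|---|
| 0.3 | 0.24 | 1.67 | 39% |
| 0.5 | 0.40 | 2.79 | 80% |
| 0.8 | 0.64 | 4.46 | 99% |

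Section 11.4 lists age, not cohort, as a covariate. In 4,000 simulated trials with group and linear age (ages assumed uniform within cohort), the mean coefficient was 0.37 SD with 73% rejection at d = 0.5, and 0.59 SD with 99% at d = 0.8. The 1A v 1B test alone rejected in 4% to 5% of these trials, as it should. Age adjustment therefore does not separate the two contrasts.

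**Case B: effect d in cohort 1, zero elsewhere.** Common coefficient = d × 10/49; z = d × 10/7.

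| d (SD) | Coefficient | Power, common coefficient | Power, 1A v 1B (t-test, 20 v 20) |
|---|---|---|---|
| 0.8 | 0.16 | 21% | 69% |
| 1.0 | 0.20 | 30% | 87% |

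**What cohort 1 can detect.** A two-sample t-test of 20 v 20 reaches 80% power at 0.91 SD.

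**Testing whether the two coefficients differ.** The SE of the difference is √(1/10 + 1/39) = 0.354. Differences of 0.5, 0.8 and 1.0 SD are detected with 29%, 62% and 80% power. A non-significant interaction would therefore not justify merging the coefficients.

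**The case against.** The strongest reply is that the plan never says the group coefficient is a priming effect. Section 11.4 calls it the size of the group effect. Section 2.2 opens with a broader hypothesis, that vaccination and infection drive immunity differently, and the primary objective covers infection and vaccine history generally. Infection versus vaccination in experienced children is therefore a legitimate aim. This stands.

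A reader might infer three stronger things that the documents do not support:

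- *That recall will be reported as priming.* Neither the label nor the word pooled appears. Both are inferred from a single G(i) and from the absence of an assigned analysis.
- *That the plan has no way to examine priming.* The time-specific tests by age and exposure could include 1A v 1B, vaccination history is collected (Section 8.1), and the covariate list is open-ended. The gap is one of specification.
- *That all 180 children in cohorts 2 to 4 give a recall contrast.* Prior vaccination is required only in 2A to 4A. A young unvaccinated child in 2B may be meeting influenza for the first time. This makes G(i) more mixed and no easier to read as priming.

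The magnitudes are also open to challenge: they use one time point, unadjusted 5% and assumed effects, and the 80% figure needs cohort adjustment that the model does not list. Hence the range of 73% to 80%.

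Finally, 1A v 1B is not a clean contrast. Its first post-vaccination sample in 1A follows the second dose, and nothing in Sections 5.1 or 5.2 bars prior vaccination in 1B. Section 2.2 requires 1A to be unexposed, but Section 5.1 does not list this.

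**Conclusion.** The point holds as a mismatch between the question in Sections 2.2 and 11.1 and the variable tested in model (0.1). Cohort 1 supplies about 20% of a cohort-adjusted common coefficient; this follows from the planned sizes alone. The rejection and power figures rest on the assumed effects and show that the error can run in both directions. They are not error rates of the plan. The study is exploratory and stratification by exposure history is already named, so this is a change that should be made to the analysis plan, not a flaw in the design.

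**What to change.** In Section 11.4, with matching wording in Section 11.1:

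1. Give G(i) separate coefficients for cohort 1 and for cohorts 2 to 4, with cohort main effects so that the first is a within-cohort contrast.
2. Name 1A v 1B, in season 1 and at the season 2 re-challenge, as the priming contrast.
3. In cohorts 2 to 4, add recorded prior vaccination and known prior infection as a covariate or stratum, as the primary outcome's stratification implies. Splitting G(i) alone leaves history unaccounted for.
4. Label the cohort 2 to 4 coefficient *most recent exposure, infection v vaccination*. Do not report a four-cohort coefficient as an effect of priming.
5. State the limits. 20 v 20 detects about 0.91 SD at 80% power, before FDR adjustment and missed blood draws. 1A is sampled after vaccination only once its second dose is given. In season 2, Section 7.3 gives a second dose to B-cohort children under 9 without two prior doses, so dose number may also differ between 1A and 1B. Flag previously vaccinated 1B infants, or remove them in a sensitivity analysis.

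The cost is wording, one extra coefficient and a history variable built from data already collected. No visits, samples or children are added. The downside is that the priming claim then rests openly on about 40 children.

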6.2 Dosage, Preparation and Administration of Study Intervention Product

All influenza vaccines will be administered at the recommended doses for age [33]:

[figure not shown]
- IIV: Fluzone 0.25 mL administered intramuscularly to children between 6 and 35 months of age enrolled in the 2018-19 influenza season.

- IIV: Fluzone 0.25 mL or 0.5 mL per 2019 ACIP guidelines administered intramuscularly to children between 6 and 35 months of age enrolled during or after the 2019-20 season
- IIV: Fluzone 0.5 mL administered intramuscularly to children 36 months of age and older

Previously unvaccinated children 6 months to <9 years of age require 2 doses of seasonal influenza vaccine at an interval of at least 4 weeks. Eligible children <9 years of age who have properly received two or more doses of seasonal influenza vaccine in the past are recommended to receive one dose per season thereafter (see Figure 1).

Figure 1:

Number of seasonal influenza vaccine doses for children 6 months through 8 years of age.

^a The 2 doses need not have been received during the same season or consecutive seasons. ^bReceipt of LAIV4 in the past is still expected to have primed a child's immune system, despite recent evidence for poor effectiveness. This is the protocol initiated for 2018-19 influenza season, which should be similar to recommendations released for future influenza seasons with the exception that the cut off year will shift to the current influenza season year.

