11.4 Final Analysis Plan

Data will be analyzed at the end of the study, with results available for publication at that time.

A cohort of n=20 to 60 healthy children that receive a prime-boost vaccination with IIV and n=20 children infected with influenza acutely will be recruited for each age cohort. Their T cell and antibody responses will be measured at three time points: baseline, day 8, and day 24 post-vaccination. We will apply Shapiro-Wilk's test to check the normality. If the data passes the normality test, two sample *t*-tests will be used to detect significant mean difference between the children of different ages and flu exposures at each time point. Otherwise, Wilcoxon rank-sum test will be used. For follow up visits, subjects will be followed longitudinally for one to two years with yearly revaccination with IIV. CD4 T cell responses (flow cytometry) and B cell and antibody responses will be measured at three time points: prior to IIV re-vaccination, 8 and 24 days post re-vaccination. We will apply one-way ANOVA *F*-test (or Kruskal-Wallis test, if the

normality assumption is rejected) to detect significant group differences at each time point. Because multiple response variables are used in this analysis, the p -values will be adjusted by the Benjamini-Hochberg multiple testing procedure [38] to control the false discovery rate (FDR) at the level of 0.05.

General linear models of difference or fold change in T/B cell response at following time points from baseline will be used to explore how childhood exposures affect immune responses over time, while controlling potentially confounding variables including age, sex, presence of asthma or allergies, or other acute or chronic illnesses and medications that may impact the immune response. In addition to time-specific comparisons, the following linear mixed effect model will be used to analyze data collected from all time points

$$y_{kit} = \alpha_k + \beta_{1k}G(i) + \beta_{2k}X_{kit} + \gamma_{kt} + \dot{\mathbf{0}}_{kit}. \quad (0.1)$$

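### Section 11.4 has no season term although children enrol and are re-challenged in different influenza seasons; if season shares differ between groups, arm and age-cohort comparisons could be biased

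*Combined protocol and SAP*

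**What the plan says.** **Enrolment spans at least two seasons.** Section 6.2 has one entry for "children between 6 and 35 months of age enrolled in the 2018-19 influenza season" and another for "children between 6 and 35 months of age enrolled during or after the 2019-20 season". The Protocol Summary gives "Study Duration: 3.5 years", with two seasons per child and an optional third.

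**The stimulus changes with the season.** Section 2.1 cites continuing antigenic drift as the reason for yearly vaccination and states that "IIV is produced by chemical inactivation of the H1N1, H3N2, and influenza B viral strains predicted to be circulating". Section 6.1.1 has vaccine ordered for each season. Section 2.2 adds: "All subjects will be followed through to the subsequent influenza season, at which point they will be rechallenged with IIV". The season of re-challenge is therefore fixed by the season of enrolment.

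**The analysis does not carry season.** Section 11.4 has four parts:
- two-sample t or Wilcoxon rank-sum tests at each time point, without covariates;
- one-way ANOVA or Kruskal-Wallis tests at the re-vaccination visits, without covariates;
- general linear models of change from baseline, "controlling potentially confounding variables including age, sex, presence of asthma or allergies, or other acute or chronic illnesses and medications";
- mixed model (0.1), with an arm indicator, the same clinical variables and a term indexed by time point that "is a random effect term that quantifies the time effects".

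None of these names enrolment season, calendar season, vaccine formulation or infecting strain.

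**The concern.** At a given visit, the tests pool children who met different vaccines or viruses. That does little harm if the groups compared enrolled in the same proportions each season, but nothing in the design secures this. Arm membership follows from vaccination or acute infection, not from allocation. Sections 5 and 7.1 describe arm A as recruited by letter, flyer and clinic contact. Arm B depends on the influenza that circulates, with up to 500 children screened to find 80 cases. No quota by season is stated for any arm or age cohort.

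Age cohorts may also fill at different times. Cohort 1 is replenished by each year's infants. Cohorts 3 and 4 are fixed by birth date, and under the 15-year limit in the Protocol Summary, children born in 2003 leave the eligible pool as they turn 16 during 2019.

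At stake are the infection-versus-vaccination contrast and the age contrasts in the primary CD4 T cell outcome. Section 11.2 says that trends found here will direct later studies, so a season difference read as an exposure or age effect could misdirect them.

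**Working it through.** **Inputs from the documents.** Arm A has 20 + 60 + 30 + 30 = 140 children and arm B has 4 × 20 = 80. The sum is 220, which matches section 5. Section 11.2 gives no power, effect size or SD, so there is no sample-size calculation to reproduce.

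**Assumptions, because the documents give no figures.** There are two enrolment seasons. Arm A is split 70/30 and arm B 40/60 (first/later). The later season shifts the response by d within-season SDs, equally in both arms, and there is no true arm effect.

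**Step 1: bias.** Bias = (share of B in later season − share of A in later season) × d.
- d = 0.5: (0.60 − 0.30) × 0.5 = 0.15 SD
- d = 0.8: (0.60 − 0.30) × 0.8 = 0.24 SD

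**Step 2: error rate of an unadjusted two-sided 5% test.** SE = √(1/nA + 1/nB), z = bias/SE, rate = Φ(z − 1.96) + Φ(−z − 1.96).

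| Comparison (A v B) | SE | z, rate at d = 0.5 | z, rate at d = 0.8 |
|---|---|---|---|
| 20 v 20 | 0.316 | 0.47, 7.6% | 0.76, 11.8% |
| 30 v 20 | 0.289 | 0.52, 8.1% | 0.83, 13.2% |
| 60 v 20 | 0.258 | 0.58, 8.9% | 0.93, 15.3% |
| 140 v 80 | 0.140 | 1.07, 18.8% | 1.71, 40.2% |

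**Step 3: allow for the variance that season adds.** Within an arm this is p(1 − p)d², where p is its later-season share. For 140 v 80 and d = 0.5, SE = √[(1 + 0.21 × 0.25)/140 + (1 + 0.24 × 0.25)/80] = 0.144, so z = 1.04 and the rate is 18%. For d = 0.8, SE = 0.150, z = 1.60 and the rate is 36%. The same step gives 7.5-8.7% and 10.9-14.0% within cohorts. Simulating the t-test with season counts held fixed (40,000 runs per setting) gives slightly less: 6.8-8.1% and 8.8-12.2% within cohorts, and 18% and 35% pooled. The Step 2 rates are therefore the upper end.

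**Step 4: other shares.** A separate simulation (20,000 runs per setting) put different shares of the two groups in one season, with d from 0.5 to 1.0.

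| Shares | 20 v 20 | 60 v 20 | 140 v 80 |
|---|---|---|---|
| 60% v 40% | 0.055-0.063 | 0.056-0.08 | 0.10-0.22 |
| 70% v 30% | 0.085-0.18 | 0.11-0.27 | 0.28-0.76 |
| 80% v 20% | 0.15-0.39 | 0.20-0.57 | 0.55-0.99 |

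With equal shares there is no bias and the rate is 0.026-0.045. The added variance is then 0.25 × 0.5² = 0.0625, about 6%, for d = 0.5. Adding a fixed season term brings the rate to 0.047-0.052 in every setting.

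**Step 5: precision cost of the term.** For 140 v 80 under the assumed split, 42 + 48 = 90 of 220 children are in the later season (0.409). The squared arm-season correlation is 0.30² × (0.636 × 0.364)/(0.409 × 0.591) = 0.086, so the variance of the arm effect rises by 1/(1 − 0.086) = 1.09. The cohort-level comparisons give 1.08 to 1.10.

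**The case against.** **Harm is conditional.** Bias needs both a season effect and unequal season shares, and the documents give neither. A reader might infer that the comparisons are biased; the text supports only that they could be. Section 2.1 also notes that T cells can recognise conserved epitopes, so a large season shift in the CD4 readout cannot be presumed. This stands.

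**The pooled rates are the least favourable case.** Section 11.4 describes recruitment by age cohort and the primary outcome is stratified by age. A reader might apply 19% or 40% to every test, but cohort-level rates are far lower. This stands; the pooled figures bear on analyses such as model (0.1) that combine cohorts.

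**Not every visit is exposed in the same way.** It is tempting to say that season affects the primary readout at every visit. Section 7.2 has arm A's visit 1 blood drawn before vaccination, so it cannot reflect that season's vaccine. Section 2.2 chose cohort 1 to have no earlier exposure, so prior-season background does not apply to it at entry. Change from baseline also removes part of any background difference, though not a difference in stimulus. This stands, and limits the point to post-exposure and re-challenge comparisons.

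**A common shift may not hold.** Season changes the vaccine in arm A and the infecting virus in arm B, and infecting strain is part of the exposure under study. One additive term may not capture both. This stands and shapes the fix.

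**The plan leaves room.** The covariate list is open-ended, section 5 promises to examine confounders, and section 11.2 frames the work as preparing later studies. But section 5 refers to medications and medical conditions, an open list does not pre-specify season, and the per-visit tests take no covariates. The time term in model (0.1) separates visits, not enrolment seasons at the same visit. False discovery rate control addresses multiplicity, not bias. This part does not answer the concern.

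**Conclusion.** The point holds as an omitted, readily available adjustment in section 11.4, and the sponsor should make it. It is not a demonstrated bias. The direction and size of any distortion depend on season shares and shifts that the documents do not give.

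Under the assumed 70/30 v 40/60 shares and a shift common to both arms, a 0.5 SD shift gives a 0.15 SD bias and per-test error rates of about 8-9% within cohorts and 18-19% pooled. A 0.8 SD shift gives 0.24 SD, 12-15% and 36-40%. Holding season counts fixed lowers the upper ends by about 1 to 3 points within cohorts and 1 to 6 points pooled. All are rates before false discovery rate adjustment. With equal shares the only loss is precision.

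**What to change.** In section 11.4:

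1. Add enrolment season (2018-19, 2019-20, later) as a categorical fixed effect to the general linear models and to model (0.1). As a sensitivity analysis, add a season-by-arm term or report season-specific estimates, because the stimulus differs by arm.
2. Use season-stratified versions of the per-visit tests: two-way ANOVA with group and season; the van Elteren test for two groups; and a season-stratified rank test for more than two groups, since van Elteren does not replace the planned multi-group Kruskal-Wallis test.
3. Tabulate children by arm, age cohort and enrolment season. State that season cannot be separated from the group effect where the compared groups do not overlap in season.

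The cost is SAP wording. Visit dates already identify season, so no new data are needed. Each model loses 1-2 degrees of freedom, and under the assumed imbalance the variance of the arm effect rises by roughly 9%, or about 5% in its standard error (√1.09 = 1.05). The season-by-arm analysis costs further precision, which is why it is placed as a sensitivity analysis.
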